5.4 Precautions and Restrictions

Fluid deficits should be corrected before and throughout treatment.

Nonsteroidal anti-inflammatory drugs (NSAIDs) induced prevalence of nephrotoxicity is relatively low; however, given the wide use of these agents many persons are at risk, including for example, patients with cardio-renal disease, dehydration, and the aging kidney. NSAIDs

CONFIDENTIAL

STUDY DRUG: MLN9708

SCRI INNOVATIONS STUDY NUMBER: MM 42

FINAL PROTOCOL: 11 APRIL 2014

AMENDMENT NUMBER 3: 11 FEBRUARY 2016

VERSION 4

should be avoided with impaired renal function given reported NSAID-induced renal failure in patients with decreased renal function.

5.5 Correlative Studies

For patients who participate in the exploratory biomarker research component of this study, peripheral blood samples will be collected on Days 1 (pre-dose), 4, 8, and 15 of Cycle 1 and Day 1 (pre-dose) of Cycle 2. Participating patients will include 3 patients at each dose level and 5 additional patients at the MTD.

Immune analysis from the peripheral blood will include:

- CD3+, CD4+, CD8+, CD45+, CD19+ and CD56+/CD16+ cells by fluorescence-activated cell sorting
- Regulatory T cells by intracellular staining of FoxP3 and surface staining of CD4+ and CD25+ cells
- Inflammatory cytokines including IL-1 β , IL-6, IL-8, IL-10 and TNF- α

Participating sites will process the samples, analyse them, and report data for the flow cytometric analysis. Samples for cytokine analysis will be shipped to a central laboratory for analysis. For shipment, handling, etc. of the correlative testing blood samples blood, see the Study Manual.

6. DOSE MODIFICATIONS

If toxicity occurs, the toxicity will be graded utilizing the NCI CTCAE v4.0, and appropriate supportive care treatment will be administered to decrease the signs and symptoms thereof. Dose adjustments will be based on the organ system exhibiting the greatest degree of toxicity.

Study drug will be delayed if patients develop > Grade 2 GVHD and until GVHD is \leq Grade 2. If GVHD severity returns to \leq Grade 2, study drug can be restarted at the initial dose. If GVHD recurs, hold dose until GVHD is \leq Grade 2 and restart at next lower dose level. GVHD stopping criteria during administration of study drug includes the development of Grade 3 or 4 GVHD in more 80%, 70%, or 60% of the first 10, 20, or 30 patients enrolled, respectively. Patients that do not complete one cycle of maintenance because of GVHD will be replaced. Criteria for GVHD are presented in Appendix F.

6.1 Dose Modifications Due to Hematologic Toxicity

Dose reductions or holds and initiation of supportive care are allowed as clinically indicated by the treating physician. Patients whose treatment is delayed due to toxicity will discontinue study drug or will proceed with the next cycle of treatment when toxicity has improved (as long as the toxicity resolves within 3 weeks) according to the dose modifications below. Treatment with MLN9708 will be held in any patient experiencing a DLT as described in Section 5.1.2 at any time during the study. Patients who experience a DLT in the first cycle of therapy will be discontinued from treatment with MLN9708. Dose modifications following treatment-related toxicity in subsequent cycles will be according to the dose modifications below.

Dose reductions for toxicity will be allowed. For patients in the first cohort, MLN9708 may be delayed, but not reduced. For patients in Cohorts 2 and 3, doses will first be delayed and then

CONFIDENTIAL

STUDY DRUG: MLN9708

SCRI INNOVATIONS STUDY NUMBER: MM 42

FINAL PROTOCOL: 11 APRIL 2014

AMENDMENT NUMBER 3: 11 FEBRUARY 2016

VERSION 4

reductions will be allowed based on clinical judgment of the treatment physician (see Figure 1). If persistent toxicity occurs despite dose delays and/or reductions, the patient will be removed from the study.

Any patients who require a treatment delay of more than 3 weeks due to treatment-related toxicity will be discontinued from study treatment, unless the treating physician and the Study Chair agree that continued treatment at lower doses is in the best interest of the patient.

6.1.1 Recommended MLN9708 Criteria for Beginning or Delaying a Subsequent Treatment Cycle & Dose Modifications for Treatment Associated Toxicity on Day 1 of a New Cycle

Treatment with MLN9708 will use a cycle length of 28 days. For a new cycle of treatment to begin, the patient must meet the following criteria:

- ANC must be $\geq 1,000/\text{mm}^3$.
- Platelet count must be $\geq 40,000/\text{mm}^3$.
- All other nonhematologic toxicity (except for alopecia) must have resolved to \leq Grade 1 or to the patient's baseline condition

If the patient fails to meet the above-cited criteria for initiation of the next cycle of treatment, dosing should be delayed for 1 week. At the end of that time, the patient should be re-evaluated to determine whether the criteria have been met. If the patient continues to fail to meet the above-cited criteria, delay therapy and continue to reevaluate. The maximum delay before treatment should be discontinued will be 3 weeks or at the discretion of the Principal Investigator.

Table 4 Dose Modifications Due to Hematologic Toxicities within a Treatment Cycle (Day 8 and Day 15 of a Treatment Cycle)

Event	Action ^d
Neutropenia (ANC)	
ANC <0.5 x 10 ⁹ /L (Grade 4) or febrile neutropenia	Hold dose until recovery to ≤ Grade 2 [ANC ≥1.0 x 10 ⁹ /L], then resume MLN9708 at one lower dose level ^a (if applicable ^b). Note: If resolved in ≤5 days, then resume without a dose reduction.
Recurrence of ANC <0.5 x 10 ⁹ /L (Grade 4) or febrile neutropenia	Hold ^a dose until ANC recovery to ≤ Grade 2 [ANC ≥1.0 x 10 ⁹ /L], then resume MLN9708 at one lower dose level ^a (if applicable ^b).
Thrombocytopenia	
Platelets <30 x 10 ⁹ /L	Hold dose until improvement to platelets ≥30 x 10 ⁹ /L 
 • If resolved in ≤5 days, then resume without a dose reduction^c. • If resolved in >5 days but <3 weeks, then resume dose at one lower dose level^c (if applicable^b).

^a Hold MLN9708 treatment; do at least weekly CBC with differential until toxicity resolves (ANC recovery ≥1.0 x 10⁹/L and platelets ≥30 x 10⁹/L).

^b Patients on 2.3 mg of MLN9708 will not undergo a dose reduction.

^c Re-treatment criteria = ANC recovery ≥1.0 x 10⁹/L and platelets ≥30 x 10⁹/L.

^d Any patient who requires a treatment delay of more than 3 weeks due to treatment-related toxicity will be discontinued from study treatment, unless the treating Investigator and Study Chair agree that continued treatment at lower doses is in the best interest of the patient. ANC = absolute neutrophil count, CBC = complete blood count.

6.2 Dose Modifications due to Non-Hematologic Toxicity

The dose reduction guidelines for non-hematologic toxicities are presented in Table 5.

Table 5 Dose Reductions for Grade 3 or 4 Non-Hematologic Toxicities

Criteria	Action
Peripheral Neuropathy:	
Newly developed Grade 1 peripheral neuropathy with pain, ≥ Grade 2 peripheral neuropathy	Hold MLN9708 until resolution to ≤ Grade ≤ 1 without pain or baseline
Grade 2 neuropathy with pain or Grade 3 peripheral neuropathy	Hold MLN9708 until resolution to Grade ≤ 1 without pain or baseline. Reduce MLN9708 to next lower dose (if applicable*) upon recovery.

CONFIDENTIAL

STUDY DRUG: MLN9708

SCRI INNOVATIONS STUDY NUMBER: MM 42

FINAL PROTOCOL: 11 APRIL 2014

AMENDMENT NUMBER 3: 11 FEBRUARY 2016

VERSION 4

Criteria	Action
Grade 4 peripheral neuropathy	Discontinue MLN9708.
Grade 2 rash and/or pruritis	Follow at least weekly. See Section 6.3.4 Specific Recommendations for Management of Clinical Events
Grade 3 Non-Hematologic Toxicities or recurrent Grade 3 Non-Hematologic Toxicities that do not recover to Grade < 1 or baseline within 4 weeks	MLN9708 therapy should be withheld until symptoms have resolved to \leq Grade 1 or baseline. Reduce MLN9708 to next lower dose (if applicable*) upon recovery. Note: a dose level reduction will be made either on the basis of within-cycle or for a subsequent cycle criteria, but not for both from the same cycle.
Grade 4 Non-Hematologic Toxicities	Discontinue MLN9708. Upon toxicity recovery, if the patient has received clinical benefit from therapy with MLN9708, the Investigator and the Study Chair may consider restarting therapy.

*Patients on 2.3 mg of MLN9708 will not undergo a dose reduction.

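### Table 5's first neuropathy row has no upper grade limit and conflicts with the two rows below it; secondarily, Table 4's 5-day recovery cut-off has no blood count required by day 5

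*Protocol*

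**What the plan says.** Protocol Section 6.2, Table 5, has three rows specific to peripheral neuropathy:

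- Row 1, trigger: "Newly developed Grade 1 peripheral neuropathy with pain, ≥ Grade 2 peripheral neuropathy". Action: "Hold MLN9708 until resolution to ≤ Grade ≤ 1 without pain or baseline". No reduction is stated.
- Row 2, trigger: "Grade 2 neuropathy with pain or Grade 3 peripheral neuropathy". Action: hold to a recovery target of Grade 1 or less without pain, or baseline, and then "Reduce MLN9708 to next lower dose (if applicable*) upon recovery".
- Row 3, trigger: "Grade 4 peripheral neuropathy". Action: discontinue.

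A footnote exempts patients on 2.3 mg from reduction. General rows for Grade 3 and Grade 4 non-hematologic toxicity follow. The Grade 4 row says discontinue, but lets the Investigator and Study Chair consider a restart after recovery.

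Protocol Section 6.1, Table 4, covers hematologic events on Days 8 and 15. For a first Grade 4 or febrile neutropenia, the default is to resume one level lower. A note makes an exception for resolution in 5 days or fewer: "then resume without a dose reduction". The platelet row (below 30 x 10⁹/L) has two explicit branches: 5 days or fewer (no reduction), and more than 5 days but under 3 weeks (one level lower). Note a tells sites to "do at least weekly CBC with differential until toxicity resolves".

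**The concern.** A dose-modification table should send each event to one action. In Table 5, a patient with painful Grade 2, Grade 3 or Grade 4 neuropathy meets the trigger of row 1 and also that of a lower row with a different action. Two sites that follow the text faithfully can then handle identical events differently.

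Table 4 raises a smaller question of the same kind. The restart dose can depend on whether recovery took 5 days or fewer, while the required counts need not fall inside those 5 days.

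First, this bears on consistent handling of patients. Second, it bears on reporting: safety is a primary objective in both documents, up to 5 centers take part, and Table 4 in the SAP's list of tables summarises reductions and interruptions.

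**Working it through.** No stated sample size, error rate or estimate is involved, so the check sets the passages side by side.

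**Table 5.** Each grade and pain state, read literally against the three neuropathy rows:

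| State | Rows matched | Actions at 3 or 4 mg | Actions at 2.3 mg |
|---|---|---|---|
| Grade 1 with pain | 1 | hold | hold |
| Grade 2 without pain | 1 | hold | hold |
| Grade 2 with pain | 1, 2 | hold; hold then reduce | hold |
| Grade 3, with or without pain (2 states) | 1, 2 | hold; hold then reduce | hold |
| Grade 4, with or without pain (2 states) | 1, 3 | hold; discontinue | hold; discontinue |

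Grade 1 without pain matches no row. States that match a row: 1 + 1 + 1 + 2 + 2 = 7. States with conflicting actions at 3 or 4 mg: 1 + 2 + 2 = 5. At 2.3 mg rows 1 and 2 coincide, which leaves the 2 Grade 4 states.

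The cycle narrows this further. Under Section 5.1.2, Grade 3 or 4 non-hematologic toxicity in Cycle 1 that is at least possibly related is a dose-limiting toxicity (DLT), and neuropathy is not among the exceptions. Sections 5.1.2 and 6.1 end treatment for such patients. The conflict therefore matters for:

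- Grade 2 with pain, at 3 or 4 mg, in any cycle;
- Grade 3, at 3 or 4 mg, after Cycle 1, or in Cycle 1 if the event is not a DLT;
- Grade 4, after Cycle 1, on a literal reading.

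**Is there a rule of precedence?** The opening of Section 6 bases adjustments on the worst-affected organ system. That chooses between systems, not between two rows for one event. Section 6.1 allows the treating physician to hold or reduce as clinically indicated, which permits either action and selects neither. If the opening words of row 1 are read as limiting the whole row to new events, a new Grade 3 event still matches rows 1 and 2.

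**Table 4.** Assume that the recovery clock starts at the low count that begins the hold (day 0). At the minimum schedule the next count is on day 7: after a Day 8 hold, the next scheduled count in Appendix D is Day 15 (15 − 8 = 7); after a Day 15 hold, note a gives Day 22 (22 − 15 = 7). The table shows what counts at a fixed spacing can establish:

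| Days between counts | Recovery days that can be shown to be 5 or fewer | Recovery days left ambiguous |
|---|---|---|
| 1 | 1 to 5 | none |
| 2 | 1 to 4 | 5, 6 |
| 3 | 1 to 3 | 4 to 6 |
| 4 | 1 to 4 | 5 to 8 |
| 5 | 1 to 5 | none |
| 6 | none | 1 to 6 |
| 7 | none | 1 to 7 |

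At 7-day spacing a recovered count on day 7 fits a true recovery on any of days 1 to 7, so the branch for 5 days or fewer can never be documented. If the clock started before the first low count, that branch would be no easier to document. The neutropenia recurrence row has no 5-day clause and is not affected.

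**The case against.** The strongest reply is that a sensible reader applies the more specific row, above all for Grade 4, where a dedicated row says to discontinue and reading a general hold row against it is strained. Section 6.2 calls the contents of Table 5 guidelines, and Section 6.1 leaves reductions in Cohorts 2 and 3 to clinical judgment, so some variation is intended. The doubled sign in row 1's action also suggests a typing or extraction slip. Much of this is fair, and it is why the Grade 4 conflict is claimed only on a literal reading. However, the protocol does not print a specific-row rule, discretion does not make two printed actions agree, and the overlap lies in row 1's trigger rather than in the doubled sign.

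On Table 4, a reader might infer that sites may draw counts only once a week. The text does not say that: weekly is a minimum, and Sections 6.3.5 and 6.3.6 allow further testing under usual practice. The first neutropenia row also has a usable default, since the reduction applies unless early recovery is shown. What stands is narrower: no count is mandated by day 5, and the platelet row, which has two symmetrical branches, gives no default when the recovery day is unknown. The marker for note a is not on the platelet row either, although the note's text covers platelets. In Cycle 1, related febrile neutropenia and Grade 4 thrombocytopenia are DLTs, which reduces the reach of Table 4 there.

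**Conclusion.** The Table 5 conflict is real: five of seven triggering states have incompatible printed actions at 3 or 4 mg, and two of seven at 2.3 mg, before the Cycle 1 DLT rule removes related Grade 3 and 4 events in that cycle. The Table 4 gap is real but secondary. The consequence is inconsistent handling of the same event, carried into the SAP's dose-modification summary. No stated statistical figure changes.

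Three stronger readings are tempting, and the documents do not support them:

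- That the two tables cannot be applied at all. Grade 1 with pain, Grade 2 without pain and the neutropenia recurrence row each have one action for their event.
- That site practice distorts the maximum-tolerated dose or the safety profile at that dose. The dose is set on Cycle 1 DLTs (Section 5.1.3), related Grade 3 and 4 neuropathy in Cycle 1 leads to discontinuation rather than to a Table 5 reduction, and no such distortion has been shown.
- That a stated share of early recoveries would be misclassified. The documents give no distribution of recovery times, so no percentage can be defended.

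The number of patients affected cannot be estimated. Protocol Table 2 reports peripheral neuropathy in 81 of 491 patients (16%) in the oral studies, without a split by grade or pain. The verdict rests on a literal reading of the row triggers and, for Table 4, on the clock starting at the count that begins the hold.

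**What to change.** Reconcile the passages in an amendment.

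- Table 5: word the neuropathy rows so that each combination of grade and pain matches one row with one action, or print a rule saying which row prevails. State how the general Grade 3 and Grade 4 rows relate to them.
- Table 4: make the recovery cut-off and the minimum count schedule consistent, so that either side of the cut-off can be documented. Say when the recovery clock starts, what applies if the recovery day is unknown, and whether note a governs the platelet row.

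The sponsor's clinical team decides which actions, cut-off and schedule apply; this review takes no position on them. The cost is two table edits. No change to the sample size or the analysis methods is needed.

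### The 3-week limit on treatment delay in Sections 6.1 and 6.1.1 is not reconciled with the 4-week criterion and open-ended hold in Table 5 for Grade 3 non-hematologic toxicity

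*Protocol*

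**What the plan says.** **Section 6.1.** The heading is "6.1 Dose Modifications Due to Hematologic Toxicity", but the text is not confined to blood counts. A delayed patient may go on to the next cycle "as long as the toxicity resolves within 3 weeks". The limit reads: "Any patients who require a treatment delay of more than 3 weeks due to treatment-related toxicity will be discontinued from study treatment", with the exception "unless the treating physician and the Study Chair agree that continued treatment at lower doses is in the best interest of the patient".

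**Section 6.1.1.** The criteria for starting a new cycle include a non-hematologic one, which begins "All other nonhematologic toxicity (except for alopecia) must have resolved to" and ends at Grade 1 or lower, or baseline. For a patient who keeps failing the criteria: "The maximum delay before treatment should be discontinued will be 3 weeks or at the discretion of the Principal Investigator".

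**Table 4 (hematologic).** Footnote d repeats the 3-week rule and its exception.

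**Table 5 (non-hematologic).** The criterion of the Grade 3 row covers Grade 3 toxicities, or recurrent ones, "that do not recover to Grade < 1 or baseline within 4 weeks". The action begins "MLN9708 therapy should be withheld until symptoms have resolved to" and ends with a reduction to the next lower dose on recovery. The row states no maximum hold and no approver. The Grade 4 row of the same table does name the Investigator and Study Chair for a restart. Table 5 has no counterpart to Table 4 footnote d. Its only footnote says that patients on 2.3 mg are not reduced.

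**The concern.** A site managing a Grade 3 non-hematologic toxicity after Cycle 1 would look to Table 5, the table for that kind of event. There it finds a 4-week criterion, an unlimited hold and a resumption. The limit that discontinues the patient after 3 weeks of delay sits in a section headed for hematologic toxicity and in a footnote to the hematologic table. Two sites could handle the same patient differently and each point to the protocol.

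Several planned outputs depend on this:

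- Safety is a primary objective, and protocol Section 10.4.3 requires a summary of adverse events leading to treatment discontinuation.
- SAP Table 1 reports reasons for treatment discontinuation, and SAP Table 4 reports dose modifications.
- The SAP's PFS rules censor at the last evaluable tumor assessment when treatment stops for an adverse event, so the stopping decision can also reach PFS.

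With at most 38 patients planned, one patient handled differently moves a proportion by 1/38 = 2.6 percentage points.

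**Working it through.** No sample size or error rate is involved. The check sets the rules side by side and then works out when they disagree.

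**1. Does the 3-week limit reach non-hematologic toxicity?** Yes. The limit in Section 6.1 is written for any treatment-related toxicity, and Section 6.1.1 lists non-hematologic recovery among the criteria to which its 3-week maximum applies.

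**2. The rules compared.**

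| | Section 6.1 | Section 6.1.1 | Table 5, Grade 3 row |
|---|---|---|---|
| Time stated | More than 3 weeks | 3 weeks | No recovery within 4 weeks |
| What is timed | Treatment delay | Treatment delay | Toxicity without recovery |
| Default action | Discontinue | Discontinue | Hold until recovery, then next lower dose |
| Who may depart from it | Treating physician and Study Chair | Principal Investigator | Nobody named |
| Limit on the hold | 3 weeks | 3 weeks | None |

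**3. The clocks differ.** Doses fall on Days 1, 8 and 15 of a 28-day cycle, so the next cycle starts on Day 29. For a toxicity that has not resolved:

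- day the 4-week criterion is met = onset day + 28;
- delay on that day = that day − day of the first dose withheld;
- the Section 6.1 limit is passed when the delay exceeds 3 × 7 = 21 days.

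*Onset on Days 16 to 22, first dose withheld on Day 29.* The 4-week point is Day 16 + 28 = 44 to Day 22 + 28 = 50. The delay is 44 − 29 = 15 to 50 − 29 = 21 days, which is not more than 21. The patient meets the Table 5 criterion and Section 6.1 has not yet discontinued treatment.

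*Onset on Days 9 to 14, first dose withheld on Day 15.* The 4-week point is Day 9 + 28 = 37 to Day 14 + 28 = 42. The delay is 37 − 15 = 22 to 42 − 15 = 27 days. Section 6.1 has discontinued the patient by default before the Table 5 criterion is met, yet Table 5 then holds and resumes.

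The second case assumes that delay runs from the first dose withheld. If it ran only from Day 29, the delay would be 37 − 29 = 8 to 42 − 29 = 13 days, and the 21-day limit would be passed only after Day 29 + 21 = Day 50. Table 4 footnote d attaches the 3-week rule to holds within a cycle, which favors the first count, but the protocol does not define it. On either count the rules part eventually, because the Table 5 hold has no end.

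**4. What the 4 weeks modifies.** The row can be read in two ways:

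- *It qualifies every Grade 3 toxicity.* Only a toxicity unresolved at 4 weeks enters the row, and the conflict arises where the delay has also passed 21 days.
- *It qualifies only recurrent ones.* A first Grade 3 event enters the row at once, and the conflict starts as soon as the delay passes 21 days.

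**5. The lowest dose.** The Section 6.1 exception is for continued treatment at lower doses. Patients on 2.3 mg cannot be reduced, so as worded it does not fit them. Only the Principal Investigator's discretion in Section 6.1.1 could cover them.

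**6. Recovery grade.** As extracted, the row uses below Grade 1 as its trigger and Grade 1 or lower as its recovery level. A patient at Grade 1 would be unrecovered by the criterion and recovered by the action.

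**The case against.** The best case for the plan is that the texts can be read together. Table 5 offers dose-reduction guidelines and tells a site how to resume. Section 6.1 says when agreement is needed, and its exception for lower doses matches the Table 5 action. Section 6.1.1 is headed as recommended criteria and leaves room for discretion. Continuing past 3 weeks is therefore not a contradiction when an exception has been used.

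Much of this stands. The conflict is between default rules. It is not resolved, however, because the exceptions disagree on who decides, Table 5 refers to none of them, and the Section 6.1 exception does not fit 2.3 mg.

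Three stronger readings are tempting, and the documents do not support them:

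- *Table 5 allows 4 weeks for recovery.* The 4 weeks stands in the criteria column and helps define who enters the row. The hold itself has no limit.
- *The row can never operate, because Section 6.1 has always acted first.* The onset on Days 16 to 22 shows otherwise.
- *Toxicities that resolve between days 22 and 28 get opposite outcomes.* If the qualifier covers the whole row, such a toxicity has recovered within 4 weeks and does not enter it. If it covers only recurrent events, a first event has no 4-week window and the conflict does not stop at day 28.

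It is also fair to say that Cycle 1 is largely untouched. Most Grade 3 or 4 non-hematologic toxicities that are at least possibly related, and delays of 14 days or more, are DLTs there and lead to discontinuation. MTD determination is therefore little affected. The difference in recovery grade may be a typing or extraction fault: a neighboring row shows the same sign twice. It is something to check in the source and carries no weight here.

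**Conclusion.** The inconsistency is real but narrower than the bare figures of 3 and 4 weeks suggest. For Grade 3 non-hematologic toxicity, mainly in Cycles 2 to 6, a patient whose treatment-related delay passes 21 days is off treatment by default under Section 6.1. The same patient, once within the Table 5 row, is held and resumed at a lower dose with no approval stated. Onset on Days 9 to 14 is a worked instance, with 22 to 27 days of delay at the 4-week point, if delay is counted from the first dose withheld.

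The conclusion rests on the limit in Section 6.1 applying to all treatment-related toxicity, as its wording says, and on no exception having been invoked. The number of patients affected cannot be derived from the documents. The matter is worth correcting because it touches patient safety and the discontinuation and dose-modification summaries, and the correction is cheap. This review takes no position on which limit is right.

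**What to change.** Reconcile Table 5 with Section 6.1, Section 6.1.1 and Table 4 footnote d, so that these points agree or are explicitly stated to differ by toxicity type:

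- the maximum delay;
- the clock it runs on (dosing delay or duration of toxicity) and when that clock starts;
- the recovery grade, after checking the signs in Table 5 against the source;
- who may approve an exception, and how the exception works for patients on 2.3 mg.

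Say also whether the 4 weeks in Table 5 applies to all Grade 3 events or only to recurrent ones. The sponsor must decide which rule applies. The drafting cost is a few lines of wording in a protocol amendment, with no change to the sample size or the planned analyses.
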